8.5 Randomization

Vaccination group and vaccine assignment allocation will be performed at the Day 1 visit as described in [Section 6.2](#). The confirmation for study vaccine administration must be recorded on the Injection page of the eCRF.

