The mITT Set consists of all participants in the FAS who provide any follow-up for ILI beginning at least 14 days following administration of study intervention. Participants will be analyzed according to the group to which they are randomized to.

The mITT Set is the primary population for the analysis of efficacy data.

PP Set for Efficacy

The PP Set for Efficacy consists of all participants in the mITT Set who have no significant protocol deviations that impact key or critical efficacy data. Participants will be analyzed according to the group they are randomized to.

Immunogenicity Set

The Immunogenicity Set consists of all participants in the FAS who have baseline and Day 29 antibody assessment via HAI assay. Participants will be analyzed according to the group to which they were randomized.

PP Immunogenicity Set

The PP Immunogenicity Set includes all participants in the Immunogenicity Set who received planned dose of IP, complied with the immunogenicity testing schedule, and had no significant protocol deviations that impact key or critical data. Participants with RT-PCR-confirmed influenza between Days 1 to 29 will be removed from the PP Immunogenicity Set.

The PP Immunogenicity Set is the primary population for the analysis of immunogenicity data in the study unless specified otherwise. Participants will be analyzed according to the group to which they are randomized to.

For PP Set for Efficacy and PP Immunogenicity Set, the following major dosing error ranges for planned mRNA-1010 and active comparator will be used to determine participant exclusion from the analysis populations:

Table 3 Exclusion Criteria for Dosing Errors

Actual Vaccine Received	Planned (mRNA-1010 50 µg)
mRNA-1010 ≤ 37.5 µg	Yes ¹
mRNA-1010 >37.5 µg – 62.5 µg	No
mRNA-1010 > 62.5 µg	Yes
Active Comparator ²	Yes

1. Yes means major dosing error
2. Active comparator is Fluarix Tetra (pre-filled syringe)

Table 4 Major Dosing Errors for Active Comparator

Actual Vaccine Received	Planned (Active Comparator²)
Fluarix Tetra ≤ 45 µg	Yes ¹
Fluarix Tetra > 45 µg – 60 µg	No
Any mRNA-1010	Yes

1. Yes means major dosing error
2. Active comparator is Fluarix Tetra (pre-filled syringe)

Solicited Safety Set

The Solicited Safety Set consists of all randomized participants who received any study vaccination and contributed any solicited AR data, i.e., had at least one post-baseline solicited safety assessment.

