6.1 General Considerations

Study Schedule of Events is presented in [Section 9.1](#).

Continuous variables will be summarized using the following descriptive summary statistics: the number of participants (n), mean, standard deviation (SD), median, minimum (min), and maximum (max).

Categorical variables will be summarized using counts and percentages.

For the summary statistics of all numerical variables unless otherwise specified, the display precision will follow programming standards. Variable display standards are presented in [Section 9.2](#).

When count data are presented, the percentage will be suppressed when the count is zero to draw attention to the non-zero counts. A row denoted "Missing" will be included in count tabulations where specified on the shells to account for dropouts and missing values. The denominator for all percentages will be the number of participants in that vaccination group within the analysis set of interest, unless otherwise specified.

Baseline value is defined as the most recent non-missing measurement (scheduled or unscheduled) collected before vaccine injection, unless otherwise specified. For immunogenicity tests and NP swab tests, the baseline is defined as the most recent non-missing result/measurement (scheduled or unscheduled) collected before or on the date (and time, if applicable) of injection (Day 1).

Age: unless otherwise specified, age is calculated as the age at screening. In the analyses for subgroups defined by age, age at screening will be used for derivation of age groups.

Vaccination groups:

The following vaccination groups will be used for summary purposes:

- mRNA-1010 50 ug
- Fluarix Quadrivalent 60 ug

All analyses and data summaries/displays will be provided by vaccination group using appropriate analysis population, unless otherwise specified. Summaries may also contain a display for all vaccination groups pooled together (i.e., overall group).

Study day relative to injection will be calculated as below:

- Study day prior to injection will be calculated as: date of assessment/event – date of injection.
- Study day on or after the date of injection will be calculated as: date of assessment/event – date of injection + 1.

Unscheduled visits: Unscheduled visit measurements will be included in analysis as follows:

- In scheduled visit windows per specified visit windowing rules
- In the derivation of baseline/last on-treatment values

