6.4.1.1 Endpoint Definition/Derivation

If ILI symptoms have been reported from Day 1 to Day 361 (Month 12)/EoS, the investigator must contact the participant to assess symptoms using the ILI eCRF and ensure an NP swab is collected if the participant's symptoms meet the criteria for protocol-defined ILI or CDC-defined ILI. Detailed description of protocol-defined ILI and CDC-defined ILI are presented in [Section 3.2](#).

Both central laboratory RT-PCR results and local certified RT-PCR results will be used for case confirmation. More specifically, the following rules apply:

1. If at least one RT-PCR positive result is reported by either the central laboratory or a local certified laboratory, the RT-PCR result is considered as positive
2. The test collection date/time of positive result will be used in the analysis

CCI

CCI

Analysis of vaccine efficacy of RT-PCR-confirmed protocol-defined ILI are as follows:

The number and percentage of participants with RT-PCR-confirmed protocol-defined ILI will be summarized by vaccination group.

The incidence rate will be provided by vaccination group, calculated as the number of participants with a case (ie, first occurrence of ILI at least 14 days after the study injection through Day 181/end of influenza season) divided by the total person-time (years). The 95% CI of the incidence rate will be calculated using the exact method (Poisson distribution) and adjusted by person-time.

The relative vaccine efficacy (rVE) will be estimated by 1- the ratio of incidence rates (mRNA-1010 vs. active comparator) adjusting for person-time, multiplied by 100:

$$\text{rVE} = 100 \times \left(1 - \frac{\text{Incidence rate in mRNA-1010 group}}{\text{Incidence rate in active comparator group}}\right) \%$$

The estimated rVE of mRNA-1010 vs. active comparator will be provided with its 95% CI computed using the exact method conditional upon the total number of cases adjusted by the total person-time.

The person-time is calculated as the time from randomization to the date of the first episode for participants with a case, or the time from randomization to the date of discontinuation or death or Day 181/end of influenza season (whichever occurs later), whichever occurs first, for participants without a case.

The other secondary efficacy endpoints will be analyzed using similar methods:

- RT-PCR-confirmed CDC-defined ILI
- RT-PCR-confirmed protocol-defined ILI in participants aged 50 years and older

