6.5 Multiplicity Control

To control the overall type I error at 0.05 level for the study, a hierarchical testing strategy will be applied to test the four null hypotheses defined in [Section 4.2](#) in the following order.

Step 1: Test null hypotheses H_0^1 and H_0^2 at 2-sided 0.025 level respectively.

If both null hypotheses H_0^1 and H_0^2 in Step 1 are rejected, the following steps will be performed at a two-sided $\alpha_1=5\%$ level. If only null hypothesis H_0^1 is rejected, the following steps will be performed at a two-sided $\alpha_1=2.5\%$ level.

Step 2: Test null hypothesis H_0^3 at α_1 level, if at least null hypothesis H_0^1 in Step 1 is rejected.

Step 3: Test null hypothesis H_0^4 at α_1 level, if the null hypotheses in Step 1 and Step 2 are all rejected.

Step 4: Test null hypothesis H_0^5 at α_1 level, if the null hypotheses in Step 1, Step 2, and Step 3 are all rejected.

The testing sequence can only continue to the next step if all prior steps achieve statistical significance at the specified α_1 level (per Step 1). If a step fails to demonstrate statistical significance at the specified α_1 level (per Step 1), then the testing sequence will stop, and all steps thereafter will not be conducted. Detailed descriptions are presented in Section 9.2 and Section 9.6.2 in Protocol Amendment 2.

All other endpoints are not controlled for multiplicity and the analyses are descriptive in nature.

The study success can only be declared if non-inferiority of mRNA-1010 vs. active comparator is demonstrated for both A strains and B strains on GMT ratio and SCR.

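### Efficacy person-time starts at randomisation, 14 days before any episode can count, so each arm's incidence rate and exact CI are about 8% low at Day 181; rVE is practically unchanged

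*SAP*

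**What the plan says.** SAP 6.4.1.1 defines a case for the incidence rate as the "first occurrence of ILI at least 14 days after the study injection through Day 181/end of influenza season". It divides the number of participants with a case by total person-time in years. The start of that person-time is given as follows: "The person-time is calculated as the time from randomization to the date of the first episode for participants with a case". Participants without a case also start at randomisation. They are followed to discontinuation, death or "Day 181/end of influenza season (whichever occurs later), whichever occurs first, for participants without a case". Protocol 9.5.2 and the protocol synopsis use the same starting point, and they describe the denominator as participants at risk, adjusted by person-time.

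For each group the SAP then plans an interval: "The 95% CI of the incidence rate will be calculated using the exact method (Poisson distribution) and adjusted by person-time". The rVE is one minus the ratio of the two rates, with an exact interval conditional on the total number of cases. The same method applies to the CDC-defined endpoint and to the 50+ and 65+ endpoints. It is repeated in the PP Set for Efficacy.

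Three other places fix the timing:

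- Protocol 8.5: "Vaccination group and vaccine assignment allocation will be performed at the Day 1 visit". SAP 4.1 places the injection on Day 1 as well.
- SAP section 5 limits the mITT Set to FAS participants "who provide any follow-up for ILI beginning at least 14 days following administration of study intervention".
- SAP 6.1 numbers the injection date as study Day 1, so Day 181 is 180 days after injection.

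**The concern.** The numerator and the denominator cover different periods. An influenza episode can occur in the first 14 days, but it cannot be counted, so those days are not time at risk for this endpoint. mITT membership requires follow-up beyond that point, so every analysed participant contributes the full 14 days. No readable text subtracts them.

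Person-time, the incidence rate and its exact interval are planned outputs for each group. A reader will take the rate as that of the stated endpoint over its stated window, and it is lower than that. The shortfall always runs in the same direction and depends on the length of follow-up, so rates over different follow-up lengths are not diluted equally. The rVE is less exposed, because both arms gain the same days per person.

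**Working it through.** **Figure to reproduce.** The documents state no attack rate, case count, incidence rate or power for efficacy, so there is no planned efficacy figure to match.

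**Inputs from the documents.** Person-time starts on Day 1 and countable cases start 14 days after injection (SAP 6.4.1.1). There are 3000 participants per arm (SAP 4.1). Follow-up ends T days after injection: T = 180 at Day 181, or later if the season ends later. T = 360 (Day 361) is the limit of follow-up.

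**Assumptions.** No dropout, cases spread evenly from day 14 to T, a 365.25-day year, and the case counts shown.

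**Step 1: general size.** For a participant without a case, the planned rate divided by the rate from day 14 is (T − 14)/T.

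| T (days) | (T − 14)/T | Planned rate low by | Corrected rate higher by |
|---|---|---|---|
| 180 | 166/180 = 0.922 | 7.8% | 8.4% |
| 210 | 196/210 = 0.933 | 6.7% | 7.1% |
| 240 | 226/240 = 0.942 | 5.8% | 6.2% |
| 360 | 346/360 = 0.961 | 3.9% | 4.0% |

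**Step 2: one arm, 60 cases in 3000 (2%), T = 180.** The mean time to a case is 14 + 166/2 = 97 days.

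- As planned: 2940 × 180 + 60 × 97 = 535,020 days = 1464.8 person-years. The rate is 60/1464.8 = 40.96 per 1000.
- From day 14: 535,020 − 3000 × 14 = 493,020 days = 1349.8 person-years. The rate is 60/1349.8 = 44.45 per 1000.
- The planned rate is low by 42,000/535,020 = 7.9%. The corrected rate is 8.5% higher.

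The exact Poisson limits for the count are divided by the same person-time, so they scale by the same factor.

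| T (days) | Planned rate per 1000 PY (exact 95% CI) | From day 14 (exact 95% CI) |
|---|---|---|
| 180 | 40.96 (31.26–52.73) | 44.45 (33.92–57.22) |
| 240 | 30.73 (23.45–39.55) | 32.65 (24.92–42.03) |
| 360 | 20.49 (15.63–26.37) | 21.33 (16.27–27.45) |

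At T = 180, an attack rate of 0.5% gives 10.17 v 11.03 (7.8% low) and 4% gives 82.69 v 89.81 (7.9% low).

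**Step 3: rVE, T = 180, 60 (mRNA-1010) v 75 (comparator) cases.** Comparator person-time as planned is 2925 × 180 + 75 × 97 = 533,775 days. Counted from day 14 it is 491,775 days.

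- As planned: 1 − (60/75) × (533,775/535,020) = 1 − 0.8 × 0.99767 = 20.19%, 95% CI −13.59 to 44.13.
- From day 14: 1 − 0.8 × (491,775/493,020) = 1 − 0.8 × 0.99747 = 20.20%, 95% CI −13.57 to 44.14.

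The interval takes Clopper-Pearson limits for the mRNA-1010 share of all cases and scales them by the person-time ratio. That ratio is almost the same under either start date.

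**Step 4: wider assumptions.** The comparator attack rate was varied from 1% to 10%, dropout from 0% to 15% and true rVE from −20% to 60%. The planned arm-level rates were then 7.8–8.9% low at Day 181 and 3.9–4.5% low at 360 days. The largest change in rVE was about 0.1 percentage point (59.84% v 59.94%), and in a confidence limit about 0.13.

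**The case against.** The strongest reply is that this is a declared convention. The start of person-time is explicit and identical in the synopsis, protocol 9.5.2 and the SAP, so a careful reader knows the rate is per person-year from randomisation. It is low only against a different denominator. It is true that the documents do not contradict each other. But consistency does not make the two parts of the rate cover the same period, and the protocol's own description of the denominator is participants at risk.

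The second reply is that nothing important depends on it. This stands. The efficacy objective is relative, and rVE does not move materially. SAP 6.5 says of everything outside the test sequence: "All other endpoints are not controlled for multiplicity and the analyses are descriptive in nature". In each tabulated scenario the corrected rate lies inside the planned interval.

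Third, the 360-day value corresponds to no planned rate, since these endpoints stop at Day 181 or season end. It serves only as the lower bound on the dilution.

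Fourth, SAP section 1 reserves SAP changes for non-principal matters arising from information that was not available when the protocol was finalised, and this change rests on no new information. That is a fair procedural point and a reason to record the departure openly.

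Fifth, moving the start date does not settle whether a participant with an episode before day 14 can later have a first episode. The readable text does not answer this, and part of SAP 6.4.1.1 is redacted. It is a separate question. The person-time rule itself is legible and complete.

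**Conclusion.** The concern holds as a minor correction. Relative to the period in which a case can count, each arm's incidence rate and both exact limits are about 8% low if follow-up ends at Day 181, and less if the season ends later, down to about 4% at the 12-month limit. Dropout or higher attack rates raise the Day 181 figure to at most 8.9% in the scenarios examined. The percentages follow from 14/T. The absolute rates, case counts, attack rates and dropout are assumptions, because the documents give none for efficacy. The rVE and its interval change by about 0.1 percentage point at most. No hypothesis test, success criterion or study conclusion is affected.

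**What to change.** In SAP 6.4.1.1, start person-time 14 days after the study injection (study Day 15) for participants with and without a case, and leave the end of follow-up as it is. Apply this to the protocol-defined, CDC-defined, 50+ and 65+ endpoints, in both the mITT Set and the PP Set for Efficacy. Do not exclude participants with an episode before that date; the analysis sets stay as defined.

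Record the difference from protocol 9.5.2 in SAP section 7, which currently lists no changes. SAP section 1 provides that the SAP governs where the two documents differ.

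The cost is one start date in the derivation and one line of documentation. It needs no new data and does not affect sample size or the alpha sequence. Reported rates rise by about 4% to 8.5% under the no-dropout assumptions, depending on when follow-up ends.

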6.4.2 Analysis of Exploratory Efficacy Endpoints

As an exploratory analysis, the following endpoints will be summarized:

- The number of participants aged 65 years and older with any episode of RT-PCR-confirmed protocol-defined ILI by baseline frailty status (categorized as Fit: 0-3, Vulnerable: 4-5, Frail: 6 or more)

- The number of participants with cases of RT-PCR-confirmed protocol-defined ILI cases that begin at least 14 days post-vaccination through Day 361 (Month 12)/EoS caused by any strain of influenza virus regardless of antigenic match to the strains selected for the seasonal vaccine

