Abbreviations: AE = adverse event; AESI = adverse event of special interest; AR = adverse reaction; CDC = Centers for Disease Control and Prevention; EoS = end of study; GMFR = geometric mean fold rise; GMT = geometric mean titer; HA = hemagglutinin; HAI = hemagglutination inhibition; ILI = influenza-like illness; MAAE = medically attended adverse event; MN = microneutralization; nAb = neutralizing antibody; RT-PCR = reverse transcription polymerase chain reaction; SAE = serious adverse event.

Other exploratory objectives are as follows:

- To explore the number and percentage of participants aged 65 years and older with first episode of protocol-defined ILI by baseline frailty status.
- To describe EuroQoL 5-dimension 5-levels (EQ-5D-5L) health questionnaire utility score at regular intervals as well as for participants with protocol-defined ILI.
- To describe Work Productivity and Activity Impairment Questionnaire: Influenza-like Illness (WPAI:ILI) v2.0 impairment percentages for absenteeism, presenteeism, work productivity loss, and activity impairment for participants with protocol-defined ILI.

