9.5.4 Exploratory Analyses

Any protocol-defined and/or CDC-defined ILI cases will be presented by vaccination group.

The number and percentage of participants aged 65 years and older with first episode of protocol defined ILI will be presented by baseline frailty status for each vaccination group.

Analyses of the other exploratory endpoints will be described in the SAP.

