2.3 Exploratory Objectives

The exploratory objectives of the study are:

- To evaluate the humoral immunogenicity of mRNA-1010 to that of the active comparator against vaccine-matched or vaccine-mismatched influenza A and B strains, including the use of alternative methods
- To further characterize the immune response to mRNA-1010 and active comparator
- To describe the occurrence of clinical influenza cases throughout the study period

Other Exploratory Objectives are as follows

- To explore the number and percentage of participants aged 65 years and older with first episode of protocol-defined influenza-like illness (ILI) by baseline frailty status
- To describe EuroQoL 5-Dimension 5-Levels (EQ-5D-5L) health questionnaire utility score at regular intervals as well as for participants with protocol-defined ILI
- To describe Work Productivity and Activity Impairment Questionnaire Influenza-like Illness (WPAI:ILI) v2.0 impairment percentages for absenteeism, presenteeism, work productivity loss, and activity impairment for participants with protocol-defined ILI.

3 Study Endpoints

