virus regardless of antigenic match to the strains selected for the seasonal vaccine, in participants aged 50 years and older or 65 years and older.

- First episode of RT-PCR confirmed Centers For Disease Control and Prevention (CDC)-defined ILI that begins at least 14 days post-vaccination through Day 181/end of influenza season caused by any strain of influenza virus regardless of antigenic match to the strains selected for the seasonal vaccine.

A CDC-defined ILI is defined as body temperature $\geq 37.8^{\circ}\text{C}$ (100°F) accompanied by cough and/or sore throat.

An RT-PCR-confirmed CDC-defined ILI is defined as a positive influenza result on a respiratory sample by RT-PCR performed at the Global Central Laboratory and/or a local certified laboratory within 7 days of onset of CDC-defined ILI at any time during the study period.

The exploratory endpoints are:

- GMT and GMFR of neutralizing antibodies (nAbs) by assays such as microneutralization (MN) assays and/or HAI assays or alternative methods against vaccine-matched or vaccine-mismatched strains on Day 29 compared with Day 1 (baseline)
- GMT and GMFR of anti-HA antibodies by HAI against vaccine-matched or vaccine-mismatched strains on Day 181 and Day 361 (Month 12)
- The proportion of participants with seroconversion, and the proportion of participants with an HAI titer $\geq 1:40$ at Day 181 and Day 361 (Month 12), as measured by HAI assay
- Frequency, specificities, or other endpoints to be determined, for the further characterization of immune responses
- Number of cases of RT-PCR-confirmed protocol-defined ILI cases that begin at least 14 days post-vaccination through Day 361 (Month 12)/EoS caused by any strain of influenza virus regardless of antigenic match to the strains selected for the seasonal vaccine
- Number and percentage of participants aged 65 years and older with first episode of RT-PCR confirmed protocol-defined ILI by baseline frailty status

- EQ-5D health questionnaire utility score at regular intervals as well as for participants with ILI
- WPAI: ILI v2.0 impairment percentages for absenteeism, presenteeism, work productivity loss, and activity impairment for participants with ILI

4 Study Design

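### The frailty objective is worded for protocol-defined ILI, but the SAP endpoint and analysis count only RT-PCR-confirmed cases, and the change is not declared

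*SAP*

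**What the plan says.** Three places describe the frailty outcome by symptoms alone:

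- Protocol Section 3, other exploratory objectives: "To explore the number and percentage of participants aged 65 years and older with first episode of protocol-defined ILI by baseline frailty status".
- Protocol Section 9.5.4 plans that analysis for participants aged 65 and older with a first protocol-defined episode: "ILI will be presented by baseline frailty status for each vaccination group".
- SAP Section 2.3 repeats the objective for participants "with first episode of protocol-defined influenza-like illness (ILI) by baseline frailty status".

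Two places add laboratory confirmation:

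- SAP Section 3.2, in the exploratory endpoint list: number and percentage of participants "with first episode of RT-PCR confirmed protocol-defined ILI by baseline frailty status".
- SAP Section 6.4.2: the number of participants "with any episode of RT-PCR-confirmed protocol-defined ILI by baseline frailty status", in the categories Fit (0–3), Vulnerable (4–5) and Frail (6 or more).

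Protocol Section 9.5.4 also commits to a wider summary: "Any protocol-defined and/or CDC-defined ILI cases will be presented by vaccination group". SAP Section 6.4.2 does not repeat it.

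SAP Section 1 states that the SAP is based on Protocol Amendment 2, that it works in addition to protocol Section 9, and that it takes precedence where methods differ. SAP Section 7, on changes to the planned analysis, is marked as not applicable.

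**The concern.** Protocol-defined ILI and RT-PCR-confirmed protocol-defined ILI are separate outcomes in both documents. Protocol Section 8.11.5 and SAP Section 3.2 define the first by a symptom combination, and the second by a positive influenza result within 7 days of onset of such an illness. The protocol states confirmation where it wants it: the exploratory endpoint on clinical influenza through Day 361 specifies RT-PCR confirmation, and the frailty objective does not. The missing qualifier therefore cannot safely be read as shorthand.

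Because the SAP prevails on methods, the confirmed-case version is the one that will be programmed. The resulting table would sit under an objective that names a broader outcome. A reader of the report could take a count of confirmed influenza for a count of all protocol-defined ILI, and Section 7 would give no warning.

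**Working it through.** **Step 1. Set the five statements side by side.**

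| Place | Episode | RT-PCR required | Summary | Time window |
|---|---|---|---|---|
| Protocol 3 (objective) | first | no | number and % | none stated |
| Protocol 9.5.4 (analysis) | first | no | number and %, by arm | none stated |
| SAP 2.3 (objective) | first | no | number and % | none stated |
| SAP 3.2 (endpoint) | first | yes | number and % | none stated |
| SAP 6.4.2 (analysis) | any | yes | number | none stated |

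The substantive difference is the RT-PCR column. The others are smaller:

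- *Any* versus *first*: Section 6.4.2 counts participants, not episodes. Over one common window, a participant with any episode is a participant with a first episode, so the count is the same.
- The percentage and the split by arm missing from the 6.4.2 bullet are supplied by the general rules in SAP Section 6.1. The default denominator there is the whole vaccination group in the analysis set. For a table by frailty category in participants aged 65 and older, that default needs an explicit override.
- No frailty statement gives a window. The next bullet in Section 6.4.2 does: from at least 14 days after vaccination through Day 361.

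**Step 2. Illustrate the counts.** The plan gives no event count, attack rate, ILI rate or frailty distribution for this analysis, so there is no figure of its own to reproduce. From SAP Section 4.1: 6000 participants, 1:1 allocation, about 20% aged 65 and older.

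- Aged 65 and older: 0.20 × 6000 = 1200, or 600 per arm.
- Cells: 3 frailty categories × 2 arms = 6.
- Expected events per cell = 600 × (share in the category) × (event rate).

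The event rates and frailty splits below are assumptions.

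| Assumed split | Category | Participants per arm | Confirmed, 1–3% | Protocol-defined ILI, 10–20% |
|---|---|---|---|---|
| Equal thirds | each | 200 | 2–6 | 20–40 |
| 70/20/10 | Fit | 420 | 4.2–12.6 | 42–84 |
| 70/20/10 | Vulnerable | 120 | 1.2–3.6 | 12–24 |
| 70/20/10 | Frail | 60 | 0.6–1.8 | 6–12 |

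Widening the assumed confirmed rate to 0.5–5% gives 1–10 per cell under equal thirds. Under 70/20/10 it gives 0.3–3 in the Frail cell and 2.1–21 in the Fit cell.

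**The case against.** The best defence is that confirmed influenza is the sensible outcome for an influenza vaccine. Every secondary efficacy endpoint requires it, and protocol-defined ILI can be met by two respiratory symptoms from any pathogen. On that view the objective is loosely worded, and correcting the objective would remove the inconsistency equally well. This has force as to which outcome is more useful. It does not remove the inconsistency, because the protocol's objective and planned analysis both omit confirmation and nothing in the SAP says the outcome was narrowed on purpose.

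Four stronger readings are tempting and are not supported:

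- *The table will be too sparse to use.* This depends on rates and a frailty split that the documents do not give. Under the assumptions shown, small counts are plausible in the Vulnerable and Frail cells but not in every cell at every rate. Changing the outcome does not reliably cure it: under 70/20/10 the Frail cell has 6–12 ILI events per arm, not 20–40. SAP Section 6.1 also allows a pooled column across arms.
- *The analysis says nothing about its objective.* Confirmed cases are a subset of protocol-defined ILI, so the table answers a narrower question. It also agrees with the SAP's own endpoint list on confirmation.
- *Moving from first to any episode changes the result.* It does not change a count of participants over the same window.
- *The SAP has dropped the all-ILI summary by vaccination group.* The SAP supplements protocol Section 9 and overrides it only where methods differ. Silence is not a differing method, and the preceding efficacy subsection contains redacted text. All that can be said is that the visible SAP does not carry the summary forward.

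**Conclusion.** The mismatch is established from the text and needs no assumption: three statements call for first protocol-defined ILI, two require RT-PCR confirmation, and SAP Section 7 declares no change. As the visible SAP stands, the frailty objective as worded is not analysed, and a narrower outcome is tabulated in its place.

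The consequence is small. SAP Section 6.5 treats endpoints outside the testing hierarchy as descriptive, and no sample size, type I error allocation or success criterion depends on this table. The numerical gap between the two outcomes cannot be fixed from the documents. The illustration of 2–6 against 20–40 events per cell rests on assumed rates of 1–3% and 10–20% and on equal frailty categories.

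**What to change.** In SAP Sections 3.2 and 6.4.2:

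1. Report the number and percentage of participants aged 65 and older with a first episode of protocol-defined ILI, by frailty category and vaccination group.
2. Show the RT-PCR-confirmed subset as a second row.
3. State one time window and one denominator for both rows. The number of participants in that frailty category and arm is the natural denominator.
4. Carry the protocol Section 9.5.4 summary of protocol-defined and CDC-defined ILI by vaccination group into the SAP.
5. Record any remaining departure from the protocol in Section 7. If the sponsor wants confirmed influenza only, that is the place to say so, with the objective reworded to match.

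The cost is SAP wording, one extra row block in a planned table, and the all-ILI summary that the protocol already promises. No new data are needed: ILI symptoms are assessed on the ILI eCRF, and the Edmonton Frail Scale is collected on Day 1.
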